CYP can be referred to Victim Support by various sources, such as the police, GPs, schools, social services, charities, parents/carers or self-referrals from CYP themselves (however, parent/carer and self-referrals will not be included in this evaluation). Following a referral each CYP's safe parent/carer or CYP themselves receives a triage phone call, usually within 48 hours, where a triage officer records details about the CYP and other services the CYP is engaging with (to ensure that there is not duplication of therapeutic interventions and to consider professional overload), assesses the risks and needs, confirms their eligibility for WeMatter, provides the parents/carers and CYP with details about Victim Support's services.

The risks and needs are assessed via Victim Support's CYP Critical Discussion Tool, which considers factors such as exposure to domestic abuse, suicidal thoughts, environment, and impacts of experiences to determine whether the risk of harm is standard or high. Parents/carers and CYP are asked to update any changes regarding risks in a timely manner throughout the service. Facilitators also review the risk assessment for CYP every four weeks, and liaise with social care and early help partners to keep abreast of risks. More details about the referral and triage process (e.g. what will happen for CYP not wanting to take part or not suitable for a digital service) as well as the risk assessment and safeguarding measures can be found in the WeMatter Intervention Protocol.

The 10-week service was designed based on Rock Pool CYP Domestic Abuse Recovery Toolkit² and is entirely operated by Victim Support. The service makes use of trauma-informed cognitive behavioural therapy (CBT) techniques, incorporating activities, games and discussions that could be adapted to accommodate CYP's support needs (e.g. autism, reading difficulty). The service was designed to help CYP understand their own experiences of domestic abuse, develop healthy coping strategies and increase their feelings of safety.

² See <https://rockpool.life/course/combined-adult-children-and-young-people-domestic-abuse-recovery-toolkit/>

The service consists of one introductory and one concluding one-to-one session between a CYP and the facilitator, with eight weekly one-hour group sessions attended online between these. The eight one-hour group sessions follow a pre-determined order and structure:

1. Introductions
2. Abuse and early warning signs

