Why (theory/rationale)	To provide a safe, peer-supported environment via group sessions led by accredited facilitators for CYP, to help them process their experiences of domestic abuse in a timely way, and equip them with coping strategies to aid in their recovery.
Who (recipients)	Children and young people (CYP) between the ages of 8 and 17 who have experienced or witnessed abuse within parent's/caregiver's home but are no longer experiencing abuse or living with the alleged perpetrator.
What (materials)	Trauma-informed CBT techniques, activities, games, discussions that could be adapted to accommodate CYP's support needs (e.g. autism, reading difficulty). Non-mandatory take home activities are also included as part of the service.
What (procedures)	10-week digital intervention service: two (introduction and conclusion) one-to-one sessions and eight group sessions each targeting a different domestic abuse-related topic. Facilitators also correspond with CYP outside of the sessions to check in and encourage engagement in following sessions.
Who (provider)	Victim Support
How (format)	One-to-one introduction and conclusion sessions bookending eight digital group sessions (eight participants per group and the group members remain the same throughout the whole service). Led by two facilitators.
Where (location)	Digital sessions delivered in school or home settings for CYP referred from all local authorities across England
When and how much (dosage)	one-hour weekly meeting over 10 weeks.
Tailoring (adaptation)	Groups are adjusted according to age groups (8–12, 13–15, and 16–17), and disability and additional needs. Facilitators make adaptations to session materials based on the results of the 'all about me' assessment in the introduction one-to-one session to accommodate CYP's support needs (e.g. reading difficulty, autism). Group dynamics are taken into consideration from the initial point of risk assessment during the triage call and are also considered following the 'all about me' assessment. Facilitators manage group dynamics initially by establishing a group contract which sets out expectations throughout the sessions. During the delivery of the service, break out rooms can be used to managed CYP's behaviour throughout and facilitators are mindful of how and which activities are delivered according to the dynamics within the group.

Theory of change

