The initial theory of change (ToC) was developed during two workshops and a series of follow-up communications with input from Victim Support, Verian, Foundations and our domestic abuse expert advisers ([name] and [name]). The ToC sought to establish the mechanisms, the outputs of these mechanisms and the related outcomes, and the eventual long-term impacts of the intervention. Based on input from Victim Support, the ToC also established the contextual factors that may impact the outcomes of the intervention alongside the intended mechanisms as well as the assumptions necessary for the intended outputs. This ToC helped inform the design of the evaluation, specifically in terms of the outputs, mechanisms and outcomes that should be evaluated.

[View the theory of change here.](#)

Inputs

To deliver the intervention Victim Support needs the following inputs:

- Referral of CYP in need of support from appropriate referral sources e.g. Police, GPs, schools, social services etc.
- WeMatter staff: qualified and accredited WeMatter facilitators, triage and early intervention officers, management team, governance board
- Service resources: Rock Pool CYP Domestic Abuse Recovery Toolkit, tailored service, and Zoom access
- CYP resources: digital access (to Wi-Fi, hardware, and software) from home or school, support from parents, carers, or trusted adults, and time available to engage with the service.

Activities

There are a range of activities performed by WeMatter staff and the CYP before, during and after the intervention:

- Pre-intervention engagement includes the initial triage call to assess CYP's suitability, needs and risks, to collect relevant personal and Equality, Diversity, Inclusion, and Equity (EDIE) data, and a follow-up call by the WeMatter facilitator to obtain parental/guardian consent for their CYP to take part in the service and evaluation and to do the randomisation.
- The introductory one-to-one session between CYP and the facilitator to complete digital competency assessment, familiarise the CYP with the platform, build the CYP-facilitator relationship, and collect Week 1 outcome data.
- Eight one-hour digital group sessions based on Rock Pool CYP Domestic Abuse Recovery Toolkit, each session covering a domestic abuse related topic.

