- During the intervention CYP also complete non-mandatory home tasks before and after each session. Facilitators also provide one-to-one support when needed during the group sessions and correspond with CYP outside of sessions to check in and encourage CYP's engagement in following sessions.

- After the intervention facilitators have a concluding one-to-one session with each CYP where they will collect Week 10 outcome data and provide referral for further support if needed.

There is also a range of activities throughout the entire intervention:

- Facilitators engage with delivery sites (school, carer) to share information about support and planned sessions.
- Facilitators/other Victim Support staff provide support to parent/carers to give reassurance, advice and/or formal referral to specialist support.
- Facilitators/other Victim Support staff engage with multi-agency meetings (e.g. safeguarding/professionals' meetings) on behalf of the CYP.
- Victim Support staff provide ongoing support for the delivery of the service, including one-to-one supervision, case reviews, service audits, or safeguarding audits.
- WeMatter facilitators receive ongoing training on domestic abuse, GDPR, continued professional development from both Victim Support and Rock Pool. They also engage in team-building activities.

Mechanisms, outputs and outcomes

The evaluation team sought to answer the following questions regarding the mechanisms and outcomes of the WeMatter service.

- What are the inputs that need to be in place to produce change?
- What outcomes were considered as a priority and why?
- What are the mechanisms that lead to identified outcomes?
- What are the contextual factors that may have a moderating and/or direct effect on the outcomes?

The ToC work identified three key mechanisms for the service to successfully achieve the desired outputs and outcomes:

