The Treatment on the Treated effects will provide estimates of the effects of the service on CYP that actually participated in the WeMatter sessions. The Treatment on the Treated effects will be estimated by scaling (weighting) the ITT estimates and standard errors according to the prevalence rate of non-compliance in the treatment group, as shown in Bloom (2008).⁹ The prevalence rate of non-compliance will be defined by whether CYP attended any group sessions.¹⁰

2. Estimation of dosage-type model examining heterogeneity in experimental effects

We will also run dosage-type models examining the heterogeneity in the estimated treatment effects according to the number of WeMatter sessions individuals attend. These models will use the same estimation approach described in the primary analysis section, except that the treatment the binary treatment variable will be interacted with a count variable representing the number of sessions attended. However, statistical power may limit what we can infer from this analysis, due to the limited sample size. Furthermore, the method above does require assumptions about the functional form of the relationship between number of sessions attended and outcomes. Alternative explorative specifications might include adding a vector of interaction terms using binary variables that represent different levels of attendance (e.g. 1–2 sessions, 3–6 sessions, 7–8 sessions, or similar). Another illustrative option we may explore includes replacing the binary treatment variable altogether and assessing the association between attending sessions and the outcome variable. However, the results from this approach will need to be heavily caveated.

Assessment of data collection efficacy and reporting of statistical measures

We will examine the efficacy of the data collection procedures, considering data quality and reliability (such as levels of missingness, variable distributions, etc.). We will also report information that can help inform power calculations in future work, such as measures of variance, auto-correlation, response rates, ICCs.

⁸ Another key assumption of this method is the exclusion restriction principle, as specified by Angrist et al. (1996), which requires that those who are randomised to the WeMatter treatment group but do not comply are not affected by the WeMatter programme. This definition of non-compliance will allow us to meet this principle.

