⁹ The key assumption of this method is satisfied in our case because CYP randomised to the waitlist control group condition are unable to obtain access to the treatment condition (i.e. there are not crossovers).

¹⁰ Another key assumption of this method is the exclusion restriction principle, as specified by Angrist et al. (1996), which requires that those who are randomised to the WeMatter treatment group but do not comply are not affected by the WeMatter programme. This definition of non-compliance will allow us to meet this principle.

Contextual factors

Other contextual factors in this trial – beyond the characteristics of the CYP, their circumstances and their local area – concern the nature of the delivery of the WeMatter service. This may include, for example, the level of experience of the facilitator, how the activities are planned and organised, whether there are commonalities between child and facilitator (e.g. same sex), etc. However, this pilot study is not powered to examine variation in estimated effects according to these factors. The qualitative research described below may provide insights into the experience of participants within the service according to these aspects.

Implementation and process evaluation

Aims

The implementation and process evaluation (IPE) will complement the IE by providing contextual evidence about how the intervention was delivered, and its perceived impact on participating CYP and WeMatter facilitators. It will also inform periodic discussions about how the trial design might be iterated during the evaluation period.

The aims of the IPE for this project are:

1. To assess the extent to which the WeMatter service was implemented according to the intervention protocol, and the perceptions of staff, stakeholders, parents/carers and CYP with regard to the implementation of the WeMatter service to inform how the intervention can be improved.
2. To assess the extent to which the WeMatter service was perceived to achieve the expected outcomes.
3. To assess the theory of change underpinning the WeMatter service.
4. To assess the extent to which the trial was carried out as planned in the evaluation protocol.
5. To assess how the implementation of the trial was perceived by staff, stakeholders, parents and CYP, to inform how the evaluation design can be improved and scaled up.

Research questions

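### Footnotes 8 and 10 say that defining compliance by group attendance meets the exclusion restriction, but the protocol's own service description reaches children who attend no group session

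*Protocol*

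**What the plan says.** The Compliance part of the Analysis plan (Protocol, Impact evaluation) will consider a TOT estimate for children who took part in the sessions. The method is "scaling (weighting) the ITT estimates and standard errors according to the prevalence rate of non-compliance in the treatment group", and the compliance rule is: "The prevalence rate of non-compliance will be defined by whether CYP attended any group sessions".

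Footnotes 8 and 10 carry the same text. They say that the exclusion restriction "requires that those who are randomised to the WeMatter treatment group but do not comply are not affected by the WeMatter programme", and then: "This definition of non-compliance will allow us to meet this principle". Neither footnote attaches a condition, and no other part of the protocol qualifies the statement.

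The description of the service covers more than the groups:

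- WeMatter service section: "The service consists of one introductory and one concluding one-to-one session between a CYP and the facilitator", in addition to the eight group sessions.
- Theory of change, Activities: "The introductory one-to-one session between CYP and the facilitator to complete digital competency assessment, familiarise the CYP with the platform, build the CYP-facilitator relationship". Week 1 outcome data are collected in the same session.
- Table 1: "Facilitators also correspond with CYP outside of the sessions to check in and encourage engagement in following sessions".
- Activities running throughout the intervention: "Facilitators/other Victim Support staff provide support to parent/carers to give reassurance, advice and/or formal referral to specialist support".

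The theory of change also names a trusting relationship with the facilitator as one of three mechanisms, and it credits that relationship with part of the increase in feelings of safety.

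**The concern.** Scaling the ITT by the compliance rate assigns the whole treatment-arm effect to the compliers. That is right only if the offer did nothing for the non-compliers. The footnotes set this test for the programme as a whole, while the compliance rule looks only at group sessions. A treatment-arm child who has the introductory one-to-one and then attends no group session is counted as untouched, although the protocol presents that contact as part of the service and as serving a named mechanism.

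If this contact improves wellbeing, its benefit in non-attenders is credited to attenders and the TOT is too large. The scaled standard error gives no sign of it, because it comes from the same division. The pilot is meant to report preliminary effect sizes for planning later evaluations, so a TOT labelled as meeting its key assumption could be given more weight than it has earned.

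**Working it through.** **Inputs.** The protocol states no TOT figure, no expected non-attendance rate and no effect of contact outside the groups, so there is no stated figure to reproduce. The following are assumed:

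- c: share of the treatment arm attending at least one group session. Non-attendance 1−c is taken from 5% to 40%.
- L: effect in attenders, 0.20 SD for illustration. This is near the top of the protocol's MDES range of 0.11 to 0.21. The relative bias does not depend on it beyond the ratio g/L.
- g: mean effect of allocation in children with no group session, compared with what they would have had on the waitlist. It averages over those who had other service contact and those who had none.

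**Do the arms differ in this contact?** Controls also have a Week 1 Zoom call with a facilitator, but only for measurement: the Summary describes both of their measurements as pre-intervention, and their service begins in Week 10 (Primary outcomes). In the treatment arm the score is taken at the start of the introductory call, so the rest of that call is exposure after baseline. The concluding one-to-one is not a source of bias, because the Week 10 score is taken at its start.

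**Formula.**

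- ITT = cL + (1−c)g
- TOT as planned = ITT/c = L + g(1−c)/c
- Bias = g(1−c)/c; relative bias = (g/L)(1−c)/c

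**Worked case.** With c = 0.8, L = 0.20 and g = 0.05 (25% of L): ITT = 0.16 + 0.01 = 0.170, and TOT = 0.170/0.8 = 0.2125, which is 6.3% above 0.20.

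**Relative bias over the assumed range.**

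| Non-attendance | g = 0 | g = 25% of L | g = 50% of L |
|---|---|---|---|
| 5% | 0 | +1.3% | +2.6% |
| 10% | 0 | +2.8% | +5.6% |
| 20% | 0 | +6.3% | +12.5% |
| 30% | 0 | +10.7% | +21.4% |
| 40% | 0 | +16.7% | +33.3% |

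If g were −25% of L, the sign would reverse (−1.3% to −16.7%). If only half of the non-attenders in the worked case had any contact, g would fall to 0.025, ITT to 0.165 and TOT to 0.206 (+3.1%).

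**Would counting the introductory one-to-one as compliance be better?** If every non-attender had it, the divisor would become 1 and the TOT would equal the ITT. With c = 0.8 and g = 0.10, ITT = 0.16 + 0.02 = 0.180. The redefined TOT is then 0.180, which is 10% below the effect in session attenders; the planned TOT is 0.180/0.8 = 0.225, which is 12.5% above it. The redefined figure is a valid average over everyone contacted, but it answers a different question.

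**The case against.** The strongest case against the point has four parts.

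1. **The bias may be negligible.** A reader might infer that the TOT is simply biased. The documents do not support that: they give neither c nor g, and the bias is zero if g = 0. At 5–10% non-attendance and g at 10% of L it is only +0.5% to +1.1%. This stands, so the bias has to be stated as conditional and shown from its low end.
2. **Contact with never-attenders is partly inferred.** Check-ins are described as encouraging later attendance, the trusting relationship is described as built over the service, and triage, the consent call and a Week 1 measurement call are common to both arms. Some children may miss the introductory call as well. This limits g and means that not every non-attender is touched. It does not remove the difference in introductory content. It also has less force among the children actually analysed, because a treatment-arm child with a Week 1 score has normally had the introductory call.
3. **Any attendance is already the loosest group-based rule.** That is true, and it is a sound choice for partial attenders. The gap is only in contact outside the groups.
4. **The stakes are low.** The TOT is optional and secondary to the ITT, and the protocol says that the pilot's focus is not on robust estimates of effect. This stands.

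A reader might also infer that compliance should be redefined to include the introductory one-to-one. That does not follow. The Week 1 score is collected in that call, so compliance among analysed children would approach 100%, and the stated target is children who took part in the sessions.

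**Conclusion.** The statement in footnotes 8 and 10 is wrong as written. The group-session rule does not secure a restriction worded for the whole programme when the protocol itself lists service contact that can reach children without any group session. The size of the bias is unknown. On the assumed ranges (g at 25–50% of the effect in attenders, 5–40% non-attendance) it runs from about +1% to +33%. It is zero if contact outside the groups has no effect, and downward if that effect is opposite in sign to the effect in attenders. The definition of compliance is acceptable for its target; the unconditional claim attached to it is not. The consequence is confined to an optional secondary estimate.

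**What to change.** - Keep group attendance as the compliance rule, since it matches the stated target of children who took part in the sessions.
- Delete from both footnotes the statement that the definition meets the exclusion restriction. State instead that the TOT assumes a negligible effect of contact outside the groups, and name that contact.
- Report the TOT over a plausible range of g as (ITT − (1−c)g)/c, for g from 0 to half the effect in attenders. Setting g = kL and solving gives ITT/(c + k(1−c)). For ITT = 0.170 and c = 0.8 this is 0.2125 at k = 0, 0.170/0.85 = 0.200 at k = 0.25, and 0.170/0.90 = 0.189 at k = 0.5.
- Do not make a redefinition that includes the introductory one-to-one the main TOT, because it would nearly equal the ITT.

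The cost is a change of wording and a few lines of arithmetic on the ITT estimate and on attendance data that the protocol already plans to collect. The secondary estimate becomes more qualified and, if g is positive, slightly smaller. The primary ITT analysis does not change.

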- If a CYP does not attend the one-to-one call, the facilitator will try to get in touch with the CYP to arrange another call in the same week or as soon as possible.

We aim to regularly review and, if required, potentially test approaches to minimise these issues during the evaluation using the rapid testing approach discussed in more details in section 5.

If missingness in outcome data turns out to be severe, depending on the type or reason for missing outcome data, we will follow best practice to try to address these issues. For example, in the scenario where there are missing item responses, we will explore using multiple imputation models to impute the missing outcome responses. Otherwise, if there is evidence of differential attrition between the treatment and control group, we will construct weights that balance these groups according to individuals' characteristics (e.g. age, gender, special education needs status, ethnicity, English as additional language status, free school meal status).

While these practices can provide reasonable adjustments to address issues related to missing data, their use is controversial and is also associated with an increased risk of bias of trial estimates (e.g. see Higgins et al., 2019). Overall, this highlights the importance of monitoring attrition and finding methods to address it. Section 5 will provide more details on how we will do this.

Compliance

The main estimates above will report ITT estimates of effects of WeMatter. The ITT estimate reflects the effects of offering CYP the WeMatter services rather than the effects of actually receiving the WeMatter services. This is because it is possible that some CYP who are offered access to the WeMatter service decide not to participate in the sessions (i.e. there maybe be non-

compliers). Non-compliance will dilute the estimated effects of actually participating in WeMatter. Initially we will assess the prevalence of participant compliance by examining descriptively attendance at the provided support sessions. We will then also consider conducting two types of analyses to estimate the effects of the intervention on compliers:

1. Estimation of Treatment on the Treated (TOT) effects⁸

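### The dosage model is presented as an experimental, complier-type analysis, but its coefficient is a non-randomised association within the treated arm, and self-selected attendance is not among its caveats

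*Protocol*

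**What the plan says.** The Compliance subsection of section 3 (Impact evaluation) says the team will "consider conducting two types of analyses to estimate the effects of the intervention on compliers".

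- **Treatment on the Treated (TOT).** The ITT estimate is rescaled by the non-compliance rate (Bloom's method). A complier is a child who attended any group session. Footnotes 8 and 10 state the exclusion restriction and then say: "This definition of non-compliance will allow us to meet this principle". Footnote 9 adds that "CYP randomised to the waitlist control group condition are unable to obtain access to the treatment condition".
- **Dosage.** The heading is "Estimation of dosage-type model examining heterogeneity in experimental effects". The text moves from considering to committing: "We will also run dosage-type models examining the heterogeneity in the estimated treatment effects according to the number of WeMatter sessions individuals attend". The specification is the primary model except that "the binary treatment variable will be interacted with a count variable representing the number of sessions attended". Two limits follow, statistical power and the assumed functional form. Attendance bands are offered as an alternative. A last option drops the treatment variable and is described as an association; a sentence asking for heavy caveats follows it, without giving a reason.

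The section nowhere says that attendance is decided after randomisation or that children at different attendance levels may differ in other ways.

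**The concern.** A child's number of sessions is an outcome of the weeks after allocation. It can depend on family stability, distress, school support or liking for the group, and each of these can also affect Week 10 wellbeing. A coefficient on sessions absorbs those influences. Under a heading about experimental effects it invites a causal dose reading, and the power caveat warns only of missing a real gradient, not of finding a false one.

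The protocol has a use for such a result. Table 4 asks whether children attended enough sessions for the service to work, and section 5 lists adherence among the findings behind the full-trial recommendations.

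The exclusion restriction is a second, smaller matter. A treated child who attends no group session may still have the introductory one-to-one, which the Theory of change (Activities) says serves to "build the CYP-facilitator relationship, and collect Week 1 outcome data". Table 1 adds facilitator contact outside sessions, and the Activities list adds support to parents. Footnotes 8 and 10 nevertheless treat the restriction as met.

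**Working it through.** **1. The plan's own figures.** The protocol gives no figure for the dosage model, so the trial's stated precision is the starting point. With 47 blocks of 16 (752 in all), equal allocation and 46 degrees of freedom:

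MDES = (2.013 + 0.850) × √[ρω/47 + (1 − ρ)(1 − R²)/(0.25 × 752)]

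Column A (ρ = 0.01, R² = 0.3, ω = 0): 2.863 × √(0.693/188) = 0.174, printed as 0.17. Columns B to F give 0.114, 0.161, 0.105, 0.118 and 0.198. All six no-attrition values in Table 3 are reproduced after rounding.

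**2. What the coefficient is.** Write T for arm and S for sessions attended. Controls have S = 0 before Week 10, so T × S = S. The model has an intercept, T, S and the Week 1 score. T absorbs the difference between arms, and the coefficient on S is left to variation in S among treated children. In simulation it agreed with a regression in the treated arm alone to within 0.0001 on average.

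**3. Size when the service does nothing.** The documents give neither the attendance distribution nor its correlation r with the outcome left unexplained by the Week 1 score. Both are assumptions here.

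- *Pattern 1:* 10% attend none, 7.5% attend each of 1 to 7 sessions, 37.5% attend 8; R² = 0.3, residual SD = √0.7 = 0.837; 1,500 simulated trials.
- *Pattern 2:* sessions are 5.5 + 2.5 × a standard normal, rounded and cut to 0–8, mean about 5.3; residual SD 0.84; 2,000 simulated trials.

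| r | Pattern 1: SD per session | False positives | Pattern 2: SD per session | False positives |
|---|---|---|---|---|
| 0 | 0.001 | 5% | not run | not run |
| 0.1 | 0.026 | 41% | 0.037 | 44% |
| 0.2 | 0.052 | 94% | 0.075 | 96% |
| 0.3 | 0.080 | >99% | 0.112 | not reported |

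Hand check, Pattern 1, r = 0.1. Mean S = 0.075 × 28 + 0.375 × 8 = 5.1. Variance = 0.075 × 140 + 0.375 × 64 − 5.1² = 8.49, so SD = 2.91. The slope can be at most r × residual SD / SD(S) = 0.1 × 0.837/2.91 = 0.029; the simulation gives 0.026 because rounding and the cap at 8 weaken the link. Its standard error is 0.837/(2.91 × √376) = 0.0148. The ratio 0.026/0.0148 is about 1.8, which implies rejection in roughly two trials in five, as simulated. By symmetry, r = −0.1 gives a false negative gradient of the same size.

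Across 8 sessions, r = 0.1 corresponds to about 0.21 SD (Pattern 1) or 0.29 SD (Pattern 2). The Pattern 1 models were fitted by ordinary least squares without the group random effect.

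**4. What an instrument adds.** Instrumenting S by arm gives ITT / mean sessions. With a true effect of zero, Pattern 1 averages 0.000 per session with 4% to 6% false positives at every r. That is expected, because an ITT of zero forces it. When the service works, the estimate hides the dose pattern:

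- 0.2 SD from any one session, nothing from further sessions: about 0.035 per session.
- 0.3 SD only at 7 or 8 sessions: about 0.026 per session.

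The test is in effect the ITT test (84% rejection for both in the first case with r = 0). The column A detectable effect becomes 0.174/5.1 = 0.034 per session, or 0.043 at a mean of 4 sessions and 0.025 at a mean of 7.

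**5. Exclusion restriction.** Suppose, purely as an illustration, that 15% attend no group session but gain a quarter of the effect. TOT is then too large by the factor (0.85 + 0.15 × 0.25)/0.85 = 1.044, about 4%.

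**The case against.** The strongest reply is that this is a non-primary analysis in a pilot whose Background disclaims robust effect estimates. It is introduced as something to consider, carries some caveats, and sits beside a TOT estimate that does rest on randomisation. The model adjusts for Week 1 wellbeing, which removes part of the selection. The attendance patterns and correlations above are invented. All of this stands and limits the weight of the point. It does not make the heading correct or supply the missing caveat.

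Four stronger readings are tempting, and the documents do not support them.

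- *That an instrument repairs the dosage model.* One binary instrument cannot identify heterogeneity by sessions or attendance bands. It also needs a stronger exclusion restriction than the TOT: the whole effect must pass through session count, linearly.
- *That the bias inflates the dose effect.* Children who cope better may attend more, but children in greater need may too. The documents do not say.
- *That the pilot would set a minimum dose on this result.* Section 5 names no dose-response result or minimum dose among its findings or recommendations.
- *That TOT receipt should include the introductory one-to-one.* The Week 1 score, a model covariate, is collected in that session, so nearly every treated child analysed would count as treated and TOT would fall back towards ITT. Controls also have a Week 1 facilitator call and all families a consent call, so part of this contact is common to both arms.

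**Conclusion.** The point holds in a limited form. The dosage coefficient is a treated-arm association with attendance chosen after randomisation, and labelling it experimental or complier-based is wrong as written. That conclusion needs no assumption beyond zero control attendance, which footnote 9 states. The size does rest on assumptions: at r = 0.1, about 0.03 to 0.04 SD per session and 41% to 44% false positives with no true effect, in an unknown direction. At r = 0 there is no problem.

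The assurance in footnotes 8 and 10 is too firm, though its likely effect on TOT is small. The primary ITT analysis is untouched. This should be corrected, but it does not threaten the trial's main result.

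**What to change.** 1. Remove the words *experimental* and *compliers* from the description of the dosage and attendance-band models. Report them as non-randomised associations and name self-selected attendance as the chief limitation, ahead of power and functional form.
2. If a per-session figure is wanted, report two-stage least squares beside the Bloom TOT: sessions instrumented by random assignment, with block effects, the Week 1 score and standard errors that allow for WeMatter group. State that it is one average under linearity and exclusion, in effect a rescaled ITT, and silent on dose heterogeneity.
3. In footnotes 8 and 10, say that the exclusion restriction is assumed and may be violated by the introductory one-to-one and by facilitator contact outside sessions. Keep the any-group-session definition of compliance.

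The cost is a few sentences and, for item 2, a few lines of code. The instrumented interval is wider than that from the option that drops the treatment variable. Under Pattern 1 its standard error is 0.012. For that option, pooled over both arms, S has mean 2.55 and variance 34.5/2 − 2.55² = 10.75, so the standard error is 0.837/(√10.75 × √752) = 0.009. It is not wider than the interaction model's 0.0148.
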